Study Design and Objective(s)	
The AAMI Human Use Condition Study (HUCS) is a prospective, observational, multi-center clinical study intended to determine whether Right Ventricular (RV) lead curvature in vivo is a function of lead stiffness. The results of this study will comprise a reference dataset to be used in a new international standard for conductor flexural fatigue performance of implantable CIED (Cardiac Implantable Electrical Device) RV leads.
 
The HUCS study objectives are as follows:
 
 1. Measure dynamic in vivo curvature of RV pacing and defibrillator leads in the extravenous and intracardiac anatomy 2. Measure the relationship between lead bending stiffness and in vivo curvature 3. Assess the relationship between subject and implant variables and lead curvature
Primary Endpoints	
Three primary endpoints will assess the relationship between lead stiffness and curvature – one endpoint each for three different regions of the lead.
 
 1. In vivo cyclic curvature and mean curvature of pacing and defibrillation leads in the extravenous region will be determined during specified arm movements. 2. In vivo cyclic curvature and mean curvature of pacing and defibrillation leads in the intracardiac region will be determined during two or more cardiac cycles. 3. In vivo cyclic curvature and mean curvature of pacing and defibrillation leads in the connector region will be determined during specified arm movements. 
The relationship between lead stiffness and curvature will be evaluated for all three Primary Endpoints.

Subject Population	
The study will enroll at least 80 and up to 120 subjects with one of four different market-released lead families identified in the tables below.

	The leads are from all four CIED manufacturers participating in this protocol. Approximately 30 leads from each manufacturer's lead family will be required.		
ICD Leads of Interest	Manufacturer	Model(s)	Description
	Abbott	LDA 210Q LDA 220Q LDA 230Q	Optisure Single Coil Defibrillation Lead Optisure Dual Coil Defibrillation Lead Optisure Dual Coil Defibrillation Lead
	Medtronic	6935M	Quattro Secure Single Coil Defibrillation Lead
Pacing Leads of Interest	Manufacturer	Model(s)	Description
	Biotronik	Siello S, Solia S	Active Fixation Leads
	Boston Scientific	4452, 4453, 4456, 4457	FINELINE II/ FINELINE II Sterox Passive Fixation (polyurethane)
	Boston Scientific	4463/4464/4465 4469/4470/4471	FINELINE II/ FINELINE II Sterox EZ Positive Fixation (polyurethane)
Inclusion Criteria	
 1. Patients with RV leads included in the scope of this study whose system has been implanted for at least 3 calendar months 2. Patients at least 18 years of age and capable of providing informed consent 3. Patients who can physically perform range of arm motion and breath-holding described in the imaging protocol (section 11.1.1) 4. Patients who are willing and able to comply with instruction related to the imaging protocol 		
Exclusion Criteria	
 1. Planned lead modification 2. Patients with abandoned leads (includes: RV/RA/LV) 3. Patients undergoing second or subsequent pulse generator change 4. Patient has permanent atrial arrhythmias 5. Limited life expectancy or medical condition that would not allow completion of the study 6. Patient is known to be pregnant or breastfeeding at time of consent 7. Limited range of mobility of the implant location arm 		

	
8. Patient is unable to climb on and off an examination table unassisted9. Patients deemed hemodynamically unstable
Study Overview and Follow-up Schedule	
The study will consist of imaging sessions conducted at least 3 months post-implant. The image data will be processed using custom 3D reconstruction software to produce data for lead curvature. Subject demographic information, disease state, implant technique details (access, implant site, etc.) will be collected.
 
Enrollment → Acquire Imaging

Study Duration	Enrollment is expected to be completed in approximately 6 months; therefore, the total study duration is estimated to be approximately 12 months.
Subject Duration	The study duration for each subject is expected to be approximately one month.
Planned Number of Investigation al Sites	Up to 10 U.S. centers will participate

3. Table of Contents

1. Title Page	1
2. Protocol Synopsis	4
3. Table of Contents	7
3.1. Table of Figures	10
3.2. Table of Tables	10
4. Introduction.....	11
4.1. Background	11
4.2. Study Rationale	14
4.3. Overview of Data Acquisition and Analysis	14
4.3.1. Determine Lead Stiffness	14
4.3.2. Acquire cine fluoroscopy data (DICOM files).....	15

4.1. Background

The implantable leads are the only elements of the implantable cardioverter-defibrillator (ICD) system that are meant to last the life of the patient without repair or replacement. However, survival of ICD leads may be as low as 85% after 5 years and 60% after 8 years.¹ Like all engineered systems, implantable leads are subject to degradation and possible failure from the effects of stresses imposed by the use environment. Conductor fracture caused by metal fatigue is one of the more serious and common failure mechanisms for transvenous ICD leads.

Fatigue life can be quantified in bench tests based on the stress-life method. In fatigue testing of ICD leads and in the *in vivo* use condition, conductor stress, σ , is proportional to curvature (C) and alternating stress, S , is proportional to cyclic (alternating) curvature (ΔC). For this reason, alternating stress, S , in lead fatigue studies is customarily reported as cyclic curvature with units of cm^{-1} or inch^{-1} .

To develop physiologically relevant bench tests for conductor fatigue performance of ICD and pacing leads, valid data on *in vivo* lead motion is needed - specifically cyclic curvature (ΔC) in the intracardiac, extravenous, and connector regions. Preliminary studies have demonstrated the feasibility of acquiring these data by 3D reconstruction of bi-plane cine fluoroscopy images.^{2 3 4} However, these studies were not randomized and did not control for effects of lead routing from the pulse generator implant site to the venous access site. None were powered to provide sufficient data for the purpose defined for the present study.

The stress-life (commonly denoted "S-N" in the literature on fatigue failure of materials) method was the first approach used to understand and quantify metal fatigue. It has been the standard design method for almost 100 years. The S-N approach is still widely used in design applications where applied stress is primarily within the elastic range of the material and the resultant lives (cycles to failure) are long, such as power transmission shafts.⁵

¹ Kleemann et al, Circulation 2007;115:2474-2480

² W Baxter, N Skadsberg, et. al., New Unanticipated Insights on Peak Lead Bending During Pectoralis Flexure. HRS 2010

³ Pau, W Baxter, et. al., Lead Use Conditions Imaging: A Noninvasive Upper Thoracic and Intracardiac Lead Mechanics Investigation, CARDIOSTIM, June2014

4.2. Study Rationale

The purpose of this study is to obtain in vivo data for the dynamic flexing experienced by defibrillation and RV pacing leads in humans. This data will be used to develop an improved international standard method for evaluating fatigue performance.

The current ISO standard for fatigue performance of transvenous defibrillation leads is insufficiently sensitive, since certain leads that met this standard have demonstrated poor reliability and were ultimately withdrawn from use. A limitation of the current standard is that it does not account for stresses due to the in vivo environment.

[figure not shown]
The AAMI Cardiac Rhythm Management Committee Transvenous Cardiac Leads Working Group has developed a new methodology based on a combination of bench testing and in vivo lead curvature data. This method requires data from multiple defibrillator and pacing lead models.

The proposed study will produce the data needed to complete the development of the new standard fatigue test methodology.

[figure not shown]
4.3. Overview of Data Acquisition and Analysis

4.3.1. Determine Lead Stiffness

The funding CIED lead manufacturers will determine lead stiffness for the pacing and defibrillator leads included in this study in accordance with pre-defined requirements. (AAMI_PC_WG1_N169 Outline of Requirements for Fatigue Performance of Cardiac Rhythm Management Leads). Examples of these measurements are shown in Figure 3, and Figure 4.

Figure 3: Example Plot – Stiffness in Intracardiac Region

[figure not shown]
Arrows indicate maximum value for ΔC and corresponding stiffness for the intracardiac region.

Figure 4: Example Plot – Stiffness in Connector and Extravenous Regions

Arrows indicate maximum value for ΔC and corresponding stiffness for the intracardiac region.

4.3.2. Acquire cine fluoroscopy data (DICOM files)

For each subject, cine fluoroscopy data (DICOM files) shown in Figure 5, for the pacing or defibrillator leads will be acquired for 3 regions– the intracardiac region, extravenous region, and connector region. The intracardiac region will be imaged for two or more cardiac cycles; the extravenous region and connector regions will be imaged while the subject executes prescribed arm motions.

Figure 5: Cine Fluoroscopy Example

4.3.3. Perform 3-D reconstruction of Lead Trajectories

For each subject, cine fluoroscopy data (DICOM file) for the RV pacing or defibrillator lead will be reconstructed to generate 3D trajectories in time and spacing in accordance with the method described in AAMI_PC_WG1_N726 Methodology for 3-D Reconstruction of Lead Trajectories from Bi-Plane Fluoroscopy DICOMs. An example of a 3-D lead trajectory is shown in Figure 5.

For each lead, the maximum cyclic curvature, ΔC_{max} , and the corresponding value of lead stiffness will be determined by the lead manufacturer, for each region (intracardiac region, extravenous region, and connector region).

5. Device Description

The devices in this study are FDA approved, commercially available, Pacemaker (PM) systems and implantable cardioverter defibrillator (ICD) systems.

Pacemaker systems are composed of any approved, commercially available dual chamber or single chamber pacemaker and at least one implantable pacing lead implanted in the right ventricle. The pacing leads included in this study are listed in Table 1.

Table 1: RV Pacing Leads

Manufacturer	Model(s)	Description
Biotronik	Siello S, Solia S	Active Fixation Leads
Boston Scientific	4452, 4453, 4456, 4457	FINELINE II/FINELINE II Sterox Passive Fixation (polyurethane)
Boston Scientific	4463, 4464, 4465, 4469, 4470, 4471	FINELINE II/FINELINE II Sterox EZ Positive Fixation (polyurethane)

ICD systems are composed of any approved, commercially available dual chamber or single chamber ICD and at least one implantable defibrillation lead implanted in the right ventricle. The defibrillation leads included in this study are listed in Table 2.

Table 2: Defibrillation Leads

Manufacturer	Model(s)	Description
Abbott	LDA 210Q	Optisure Single Coil Defibrillation Lead
	LDA 220Q	Optisure Dual Coil Defibrillation Lead
	LDA 230Q	Optisure Dual Coil Defibrillation Lead
Medtronic	6935M	Quattro Secure Single Coil Defibrillation Lead

6. Required Imaging System

Center selection criteria include access to a biplane fluoroscopy system with capability of at least 15 frames per second (fps) and image portability using removable media or secure network. The following equipment must be available at each study site to support study activities;

- Biplane fluoroscopy system with:
 - capability of fluoroscopy (scout image) capture at 7.5 fps or less **and** Cine recording at 15 fps or more
 - capability of image recording in a DICOM format
 - if available, capability of simultaneous recording of the ECG signal as part of the DICOM header
- Secured Hard Drive for data storage and capabilities of nightly backup
- Computer system capable of high-speed network data transfer

7. Study Overview and Endpoints

7.1. Study Overview

The Human Use Condition Study (HUCS) is a prospective, observational, multi-center clinical study intended to determine whether lead curvature in vivo is a function of lead stiffness. The results of this study will comprise a reference dataset to be used in a new international standard for conductor flexural fatigue performance of implantable CIED leads.

The extravenous region and connector region for each subject enrolled in the study will be imaged by high resolution, bi-plane cine fluoroscopy while the subject executes prescribed arm motions. The intracardiac region will be imaged for two or more cardiac cycles.

Lead trajectories in DICOM file images will be manually identified in both views. For each frame, 3D lead trajectory will be generated using indicated 2D lead trajectories. Three dimensional reconstructions will be generated for the prescribed arm motions utilized in the imaging study.

7.2. Primary Endpoints

Three primary endpoints will assess the relationship between lead stiffness and curvature – one endpoint each for three different regions of the lead. Primary Endpoint 1 will evaluate the extravenous region. Primary Endpoint 2 will evaluate the intracardiac region. Primary Endpoint 3 will evaluate the connector region.

Failure to reject any of the null hypotheses does not indicate a failure of the study, but rather that no significant relationship between lead stiffness and lead curvature was observed. The results of the endpoint analyses will be used to inform the new lead standard.

7.2.1. Primary Endpoint 1 (Extravenous Region)

In vivo cyclic curvature (ΔC) and mean curvature (C_{mean}) of RV pacing and defibrillation leads in the extravenous region will be determined during specified arm movements. The relationship between lead stiffness and curvature will be evaluated.

7.2.1.1. Hypotheses

The following set of hypotheses will be used to evaluate the relationship between lead stiffness and curvature in the extravenous region:

$$H_0: a \geq 0$$

$$H_a: a < 0$$

[figure not shown]
where a represents the coefficient for stiffness in the following model:
 $\log(\text{curvature}) = a * \text{stiffness} + b + \text{normally distributed error.}$

Prior studies of in-vivo curvature have shown that a lognormal distribution models the data well. The alternative hypothesis represents an inverse relationship between lead stiffness and curvature.

7.2.1.2. Statistical Methods

Each lead with lead stiffness and curvature data available in the extravenous region of the lead will be included in the analysis of Primary Endpoint 1. Each lead's curvature measurement used in the analysis will represent the maximum value of the curvature observed in the extravenous region. Each lead's stiffness measurement used in the analysis will represent the stiffness measurement at the location corresponding to the maximum value of the curvature (Figure 6).

Figure 6: Curvature and Stiffness Values used Primary Endpoint 1 Analyses

Arrows indicate maximum value for ΔC and corresponding stiffness for the extracardiac region.

The relationship between curvature and stiffness will be evaluated via a general linear model, treating log (curvature) as the outcome and stiffness as the predictor. The following model will be fit: $\log (\text{curvature}) = a * \text{stiffness} + b + \text{normally distributed error}$. The 90% upper confidence limit of the coefficient for stiffness, a , will be compared to 0. If the upper confidence limit is less than 0, the null hypothesis will be rejected, thereby establishing a significant relationship between curvature and stiffness in the extravenous region.

7.2.2. Primary Endpoint 2 (Intracardiac Region)

In vivo cyclic curvature (ΔC) and mean curvature (C_{mean}) of RV pacing and defibrillation leads in the intracardiac region will be determined during two or more cardiac cycles. The relationship between lead stiffness and curvature will be evaluated.

7.2.2.1. Hypotheses

The following set of hypotheses will be used to evaluate the relationship between lead stiffness and curvature in the intracardiac region:

$$H_0: a \geq 0$$

$H_a: a < 0$

[figure not shown]
where a represents the coefficient for stiffness in the following model:
 $\log(\text{curvature}) = a * \text{stiffness} + b + \text{normally distributed error.}$

Prior studies of in-vivo curvature have shown that a lognormal distribution models the data well. The alternative hypothesis represents an inverse relationship between lead stiffness and curvature.

7.2.2.2. Statistical Methods

Each lead with lead stiffness and curvature data available in the intracardiac region of the lead will be included in the analysis of Primary Endpoint 2. Each lead's curvature measurement used in the analysis will represent the maximum value of the curvature observed in the intracardiac region. Each lead's stiffness measurement used in the analysis will represent the stiffness measurement at the location corresponding to the maximum value of the curvature (Figure 7).

Figure 7: Curvature and Stiffness Values used Primary Endpoint 2 Analyses

Arrows indicate maximum value for ΔC and corresponding stiffness for the intracardiac region.

The relationship between curvature and stiffness will be evaluated via a general linear model, treating log (curvature) as the outcome and stiffness as the predictor. The following model will be fit: $\log(\text{curvature}) = a * \text{stiffness} + b$ + normally distributed error. The 90% upper confidence limit of the coefficient for stiffness, a , will be compared to 0. If the upper confidence limit is less than 0, the null hypothesis will be rejected, thereby establishing a significant relationship between curvature and stiffness in the intracardiac region.

7.2.3. Primary Endpoint 3 (Connector Region)

In vivo cyclic curvature (ΔC) and mean curvature (C_{mean}) of RV pacing and defibrillation leads in the connector region will be determined during specified arm movements. The relationship between lead stiffness and curvature will be evaluated.

7.2.3.1. Hypotheses

The following set of hypotheses will be used to evaluate the relationship between lead stiffness and curvature in the connector region:

$$H_0: a \geq 0$$

$$H_a: a < 0$$

[figure not shown]
where a represents the coefficient for stiffness in the following model:
 $\log(\text{curvature}) = a * \text{stiffness} + b + \text{normally distributed error}.$

Prior studies of in-vivo curvature have shown that a lognormal distribution models the data well. The alternative hypothesis represents an inverse relationship between lead stiffness and curvature.

7.2.3.2. Statistical Methods

Each lead with lead stiffness and curvature data available in the connector region of the lead will be included in the analysis of Primary Endpoint 3. Each lead's curvature measurement used in the analysis will represent the maximum value of the curvature observed in the connector region. Each lead's stiffness measurement used in the analysis will represent the stiffness measurement at the location corresponding to the maximum value of the curvature (Figure 8).

Figure 8: Curvature and Stiffness Values used Primary Endpoint 3 Analyses

Arrows indicate maximum value for ΔC and corresponding stiffness for the connector

The relationship between curvature and stiffness will be evaluated via a general linear model, treating $\log(\text{curvature})$ as the outcome and stiffness as the predictor. The following model will be fit: $\log(\text{curvature}) = a * \text{stiffness} + b + \text{normally distributed error}$. The 90% upper confidence limit of the coefficient for stiffness, a , will be compared to 0. If the upper confidence limit is less than 0, the null hypothesis will be rejected, thereby establishing a significant relationship between curvature and stiffness in the connector region.

7.3. Sample Size

To sufficiently power each of the three Primary Endpoints, a total of 30 subjects enrolled for each manufacturer's lead families is expected to yield at least 20 leads with usable endpoint data in the each of the 3 image regions. Monte Carlo simulations were performed to establish the sample size, using the following assumptions:

- Expected value for coefficient $a = -0.23$
- Alpha (one-sided) = 10% (corresponding to a one-sided 90% upper confidence limit)
- Power = 99%
- Missing data = 33%

Reasons for missing data includes, imaging and/or ECG data not collected, imaging data not optimal for analysis, and subject withdrawal/death. Enrollment may stop prior to 30 subjects if 20 useable data sets have been collected.

7.4. Additional Analyses

7.4.1. Multiple Measures per Region

In addition to the Primary Endpoint analyses, in which only one measurement per region will be assessed, analyses evaluating multiple measurements per region will be performed. Curvature and stiffness measurements obtained in millimeter intervals will be evaluated. Analyses will be performed separately for each of the three regions of the lead. To account for the within-subject correlation, a random effects general linear model will be used. These analyses will evaluate the relationship between curvature and stiffness across the entire region of the lead.

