8.2. Scale and Duration

The HUCS study will enroll at least 80 and up to 120 subjects, with at least 20 and up to approximately 30 subjects per lead family specified in Section 5. Enrollment is expected to be completed in approximately 6 months; therefore, the total study duration is estimated to be approximately 12 months. The study duration for each subject is expected to be approximately 1 month to account for time from enrollment to completing the imaging protocol. Subject participation will be considered complete after image has been acquired. Up to 10 U.S. centers will participate.

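### The millimetre-level analysis in 7.4.1 does not address serial correlation along the lead; fitted as a random-intercept model, it could give standard errors well below the truth

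*Combined protocol and SAP*

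**What the plan says.** Section 7.4.1 sets this analysis beside the main ones: "In addition to the Primary Endpoint analyses, in which only one measurement per region will be assessed". On the data it says: "Curvature and stiffness measurements obtained in millimeter intervals will be evaluated". The three regions are analysed separately, and the aim is to describe the curvature-stiffness relationship over the whole of each region. Dependence within a subject is covered by one sentence: "To account for the within-subject correlation, a random effects general linear model will be used".

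Section 7.4.1 does not say whether the random part is an intercept only or also a stiffness slope. It gives no residual covariance, no standard-error method, no hypothesis, no alpha and no decision rule. The only stated error level is in section 7.3, for the primary endpoints: "Alpha (one-sided) = 10% (corresponding to a one-sided 90% upper confidence limit". Those endpoints use one point per lead and region.

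**The concern.** Points one millimetre apart on one reconstructed 3-D trajectory are neighbours on a continuous body, so their deviations from the fitted line should be alike, and less so as the distance grows. A random intercept per subject gives every pair of points on a lead the same correlation, whatever the distance, and treats what remains as independent. If stiffness also changes gradually or in blocks along the lead, the leftover correlation lines up with the predictor. Each lead is then credited with far more information on the slope than it carries.

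This is the only planned analysis that uses the whole region instead of its point of maximum curvature. Under section 12.3 the analysis report is to be codified into a new standard. Intervals that are too narrow could overstate how firmly the relationship along the lead is known.

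**Working it through.** **Number of leads.** Section 7.3 assumes 33% missing data, and 30 enrolled per family is "expected to yield at least 20 leads with usable endpoint data" in each region. Check: 20 / (1 − 0.33) = 29.9, rounded up to 30, and 30 × 0.67 = 20.1. The figure reproduces. Four families × 20 = 80 leads, the lower bound in section 8.2. The plan gives no error rate for 7.4.1, so there is none to reproduce.

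**Assumed inputs (not in the documents).** Points per region, variance components, correlation along the lead and shape of the stiffness profile. The 10% one-sided level is borrowed from section 7.3.

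**Closed-form check.** Let the residuals have lag-1 correlation r_e and the stiffness profile lag-1 correlation r_x:

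- true SE / reported SE = √[(1 + r_e·r_x) / (1 − r_e·r_x)]
- one-sided rejection under a true null = 1 − Φ(1.2816 / ratio)

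Low end, r_e = 0.5 and r_x = 0.8: product 0.40; ratio √(1.40/0.60) = 1.53; 1.2816/1.53 = 0.84; rejection 20%.

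High end, r_e = 0.95 and r_x = 0.95: product 0.9025; ratio √(1.9025/0.0975) = 4.42; 1.2816/4.42 = 0.29; rejection 39%.

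**Simulation, random intercept only.** True coefficient 0; 4 families × 20 leads; 30, 60 or 120 points per region; intercept SD 0.5; residual SD 0.6 with correlation exp(−d/ℓ) at distance d mm; smooth, step or linear stiffness; REML fit; 800 runs per cell. Ranges are over profiles and numbers of points.

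| ℓ (mm) | lag-1 correlation | true/reported SE | one-sided rejection (nominal 10%) |
|---|---|---|---|
| 0 | 0 | 0.96–1.04 | 8–12% |
| 1 | 0.37 | 1.3–1.5 | 15–20% |
| 2 | 0.61 | 1.8–2.0 | 21–28% |
| 5 | 0.82 | 2.4–3.1 | 29–36% |
| 10 | 0.90 | 2.7–4.2 | 33–38% |
| 20 | 0.95 | 2.8–5.3 | 35–41% |

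Other runs with 80 leads and 50 or 100 points, at lag-1 correlation 0.5 to 0.95, gave rejection of 20–34% (SE ratio 1.5–3.3) and 23–40% (SE ratio 1.7–4.8), depending on variance components and profile. About 1.6 to 4.8 fold and 20 to 40% is a fair summary; individual settings fall a little outside it.

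The one-sided rate cannot pass 50% however small the reported SE becomes, so the SE ratio is the better measure. A two-sided 10% test in the tabulated runs rejects 50–60% at ℓ = 5 mm.

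**Conditions that change the answer.**

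- Half the residual variance made independent noise (smooth profile, 60 points): 19%, 28% and 30% at ℓ = 2, 5 and 10 mm.
- Stiffness constant within the region: 9–12%.
- Stiffness jagged from point to point: 8–14%.
- Random intercept plus random stiffness slope, no serial term (40 points, 250 runs): 7–14%, SE ratio 0.93–1.02.
- Random intercept plus serial residual (40 points, 250 runs): 7–12%, SE ratio 0.93–1.06.
- Lead-clustered robust standard errors (80 leads, 50 or 100 points): 9–12% throughout.

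Monte Carlo error for a 10% rate is √(0.1 × 0.9/800) = 1.1 points in the tabulated runs and √(0.1 × 0.9/250) = 1.9 points in the 250-run cells.

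**The case against.** A reader might infer that a random effects model by itself makes these standard errors too small, or that the plan contains a 10% test that really runs at 20 to 40%. The documents support neither reading.

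- Section 7.4.1 does not restrict the model to an intercept. A random stiffness slope fits its wording and held close to the nominal level.
- It sets no test. The 10% belongs to the primary endpoints.
- The size of the effect depends on the stiffness profile. The example stiffness plots (Figures 3 and 4) are not reproduced in the text available, and no wording describes their shape.
- Section 8.1.5 cites a separate statistical analysis plan, AAMI_PC_WG1_N725, whose own text is not at hand. The covariance structure may be set out there.
- The analysis is headed as additional. Section 7.2 says that the endpoint analyses will inform the standard; it does not say this of 7.4.1.

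All of this stands, and it limits the claim to a conditional one. What remains is that a single sentence permits both a model that holds its level and one that can reject at two to four times that level. A random intercept is its plainest reading. Too narrow an interval is also a fault whether or not a formal test is declared.

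**Conclusion.** The point holds in conditional form. Section 7.4.1 leaves serial correlation along the lead unaddressed. Under a random-intercept fit with independent residuals, and stiffness that varies smoothly or in steps, reported standard errors would be too small by about 1.6 to 4.8 fold at lag-1 correlation 0.5 to 0.95. That corresponds to roughly 20 to 40% rejection of a true null at a borrowed one-sided 10% level. These are illustrations over assumed inputs, not properties of the plan. The inflation largely disappears with constant or jagged stiffness or with a random stiffness slope. The three primary endpoint tests and the reference dataset itself are untouched. This is a worthwhile, inexpensive clarification of an additional analysis.

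**What to change.** In 7.4.1, name the random terms, keep the lead random effect, and state that the confidence limit for the stiffness coefficient comes from robust standard errors clustered on the lead. With about 80 leads this does not depend on getting the correlation along the lead right. An acceptable alternative is a within-lead AR(1) or exponential residual indexed by millimetre position; both are not needed. If the separate statistical analysis plan already specifies such a structure, a cross-reference from 7.4.1 is enough.

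The cost is a sentence or two and a few lines of code, with no new data. The downside is wider confidence limits for this additional analysis.
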